The transition from cangrelor to prasugrel is associated with transient recovery of platelet reactivity, in particular within 1 hour after cangrelor discontinuation, which could be explained by a DDI similar to that described for clopidogrel [9]. However, it was observed that recovery of platelet function was attenuated when prasugrel was administered 30 minutes before stopping the cangrelor infusion [9]. Accordingly, it is recommended that prasugrel be administered at the end of cangrelor infusion or 30 minutes prior to discontinuation of infusion [3,4,9]. However, recently the ExcelsiorLOAD2 (Impact of Extent of Clopidogrel-Induced Platelet Inhibition during Elective Stent Implantation on Clinical Event Rate - Advanced Loading Strategies) study showed that prasugrel 60 mg LD given at the start of a 2-hour infusion of cangrelor was associated with sufficient platelet inhibition post-cangrelor, with only rare cases of high platelet reactivity (HPR) [19]. Moreover, there were no differences with levels of platelet reactivity and HPR rates compared with those observed with ticagrelor, which was also given at the start of the cangrelor infusion. These observations may be attributed to relatively higher concentration and longer half-life of prasugrel's active metabolite compared with that of clopidogrel [20-23]. However, ExcelsiorLOAD2 was not powered to test the non-inferiority on PD effects between prasugrel and ticagrelor, but only for the comparison of prasugrel versus clopidogrel. Moreover, whether similar findings would be observed with longer infusions of cangrelor (e.g., up to 4 hours) is unknown. Therefore, although the PD results of this study provide some support on the safety of administering prasugrel at the start of cangrelor infusion, the trial design does not allow to rule out a DDI given that there was no comparator arm in which prasugrel was either given alone or at the end of cangrelor infusion [24]. Moreover, pharmacokinetic (PK) assessments,

pivotal to help elucidate a DDI, were not performed. Accordingly, recommendations on timing of prasugrel administration in cangrelor treated patients remain unchanged.

STUDY RATIONALE

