Guidelines recommend the preferential use of new generation P2Y₁₂ inhibitors, including prasugrel, over clopidogrel in high-risk patients with coronary artery disease (CAD) undergoing PCI [16-18]. Since high-risk patients undergoing PCI is a setting in which cangrelor is frequently used, there is an unmet need to better elucidate PD profiles associated with the transition from cangrelor to prasugrel therapy. To date the uptake of the newer oral $P2Y_{12}$ inhibitors has been mostly limited by costs. However, prasugrel has recently gone off patent and the availability of a generic formulation will favorably impact its use. Moreover, to date PD studies assessing the transition from cangrelor to prasugrel have been conducted in patients with stable coronary artery disease, and current recommendations are based on assessments conducted in patients not undergoing PCI [9]. Importantly, acute coronary syndrome (ACS) and PCI are both known to affect PK and PD profiles of antiplatelet agents. Overall, these observations strongly underscore the need to conduct dedicated investigations to rule out a DDI when transitioning from cangrelor to prasugrel and to define the optimal approach for transitioning therapy in real-world high-risk patients, including ACS patients, undergoing PCI. The methodological approach for this assessment should rely on comprehensive PD assessments aimed to assess levels of $P2Y_{12}$ receptor inhibition, PK assessments to assess systemic levels of the drug/drug metabolite, and mechanistic assessments by measuring levels of $P2Y_{12}$ receptor gene expression. In particular, different levels of P2Y₁₂ receptor gene expression can modulate the PD effects of oral P2Y₁₂ receptor inhibitors at a given level of drug exposure defined by PK profiling.

STUDY AIM

The aim of this investigation is to rule out a DDI when cangrelor and prasugrel are concomitantly administered in high-risk patients undergoing coronary stenting.

REASERCH PLAN

Study design

[figure not shown]

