the start of PCI plus prasugrel administered at the end of the cangrelor infusion (group 3). Prasugrel will be used in line with FDA recommendations using a 60mg LD followed by a 10mg daily maintenance dose started 24 hours after LD administration [25]. Cangrelor will be used at the FDA recommended dose using a 30 μ g/kg bolus followed by 4 μ g/kg/min infusion [26]. Study drugs will be administered before passing of the guidewire. The duration of cangrelor infusion will be 2 hours or until the end of PCI (whichever is longer). All patients will be on a background of aspirin therapy (325 mg loading dose followed by 81 mg daily maintenance dose). Patients will be managed according to standard of care. The interventional procedure will also be performed according to standard of care with choice of anticoagulant (heparin or bivalirudin) at the discretion of the operator. PK and PD assessments will be conducted at 7 time points: baseline, 30 minutes after administration of randomized treatment, end of PCI (defined as when the guide catheter is removed at procedure completion), 1 hour, 2 hours, 3 hours and 4 hours after administration of randomized treatment. Figure 1 illustrates the overall study design. In patients in which the infusion will be maintained for more than 2 hours (until the end of PCI), the 3-hour and 4-hour after time points will be collected 1 hour and 2 hours after stopping cangrelor, respectively.

Although the study will have an open-label design, laboratory personnel will be blinded to treatment assignments. During hospital stay, major adverse cardiac events (death, myocardial infarction, stroke, and urgent revascularization procedures), serious adverse events (bleeding and other adverse events), as well as non-serious adverse events considered to be study related will be collected. After completing the study, decisions on medical management, including the choice and duration of antiplatelet therapy will be at the discretion of the treating physician.

Figure 1. Overall study design

Study Population

Inclusion criteria:

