3) Total Thrombus-Formation Analysis System (T-TAS): T-TAS is an automated microchip flow chamber system for the quantitative analysis of the thrombus formation process under blood flow conditions. T-TAS allows measurement of thrombus formation using the PL-chip (Diapharma, West Chester Township, OH) [34]. The PL-chip contains 25 capillary channels (width 40 μm, depth 40 μm) coated with type I collagen and is specifically designed for quantitative analysis of platelet thrombus formation, including platelet adhesion and aggregation, granule secretion, and thrombus growth in the absence of coagulation and fibrinolysis systems. In measurements using the PL-chip, a blood sample collected in a hirudin containing blood sampling tube. The platelet aggregates gradually increase in size and, in the process, occlude the capillary, resulting in an increase in flow pressure. In the present study, total platelet-derived thrombogenicity is expressed as the area under the flow pressure curve for the first 10 min for the PL-chip tested at a

flow rate of 18 μ L/min (PL18-AUC10). Low PL18-AUC10 reflect reduced thrombus growth and rapid breakdown of the thrombus.

3) Pharmacokinetic (PK) assay: Determination of prasugrel's active metabolite concentration in plasma will be performed using liquid chromatography with tandem mass spectrometry according to standard protocols as previously described [27,35]. Blood will be drawn into standard EDTA tubes and within 30 seconds a derivatizing agent (3'-methoxyphenacylbromide) will be added to capture and stabilize the active metabolite. The geometric mean area under the concentration-time curve through the sampling time of the last quantifiable prasugrel's active metabolite concentration (AUC[0-t_{last}]) will be calculated and the maximum observed plasma concentration (Cmax) and time to Cmax (Tmax) of Pras-AM will be recorded.

4) $P2Y_{12}$ gene receptor level expression: Gene expression in platelets will be performed using standard protocols. In particular, purified platelets are dissolved in Trizol reagent (Invitrogen) and total RNA will be extracted using RNA minipres kit (Zymos research) according to manufacturer's protocol. P2Y₁₂ mRNA expression will be measured with real-time PCR using SYBR green and specific primers as previously described [36].

Study endpoints, sample size calculation and statistical analysis

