The primary end point of the study will be the non-inferiority in PRU measured at 4 hours of cangrelor plus prasugrel concomitantly administered at the start of PCI versus prasugrel only administered at the start of PCI (group 2 vs. group 1). Non-inferiority will be assessed using a 95% confidence interval (CI) of the difference in mean PRU between the two arms. Under the assumption of 0 difference in mean PRU between group 1 and group 2 and a common standard

deviation of 50 PRU, a sample size of 22 patients per group will allow for the 95% CI to stay within ± 45 PRU with a 90% power and alpha=0.05. Considering a 25% data attrition rate due to GPI use, hemolysis, drop out or technical problems, 28 patients per group will need to be randomized in order to ensure complete available data for analysis. Considering the 3 arms of treatment up to 84 patients will need to be randomized. The sample size of this study was established according to results of previous PD investigations [28,37]. In line with previously reported investigations, 45 PRU was chosen for the noninferiority margin for the upper 95% CI limit of the difference [29,30]. Group 3 will be included in study design as this strategy represents current standard of care for the transition from cangrelor to prasugrel. However, the study will be powered to assess non inferiority of group 2 vs. group 1. Therefore, all other end points will be considered exploratory and will include the comparisons of PD and PK parameters, and P2Y₁₂ gene receptor level expression between all treatment arms at each time points, as well as the comparisons of rates of high on-treatment platelet reactivity (HPR). HPR will be defined as PRU>208 and PRI>50%, in line with consensus definitions [38].

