Conformity to the normal distribution will be evaluated for continuous variables with the Kolmogorov-Smirnov test. For baseline characteristics, continuous variables will be expressed as mean ± SD or median [IQR]. One-way analysis of variance or Kruskal-Wallis test will be used to compare continuous variables. Chi-squared test will be used to compare categorical variables among groups. An analysis of covariance (ANCOVA) method with a general linear model, with treatment as the main effect and baseline values of platelet reactivity as a covariate, will be used to evaluate the primary end point as well as all between-group comparisons at each time point. Least-square mean (LSM) differences in PRU between group 1 and group 2 and the corresponding 2-sided 95% CI for the difference will be obtained to assess non-inferiority based

on the ANCOVA model. Given the exploratory nature of comparisons for secondary end points, correction for multiple comparisons will not be performed. A 2-tailed p value of <0.05 will be considered to indicate a statistically significant difference for all the analyses performed. Statistical analysis will be performed using SPSS version 22.0 software (SPSS Inc., Chicago, Illinois).

The safety population will include all randomized patients exposed to study medication. The PD population will include all patients with PD data and without a major protocol deviation thought to affect significantly the PD and PK of cangrelor or prasugrel. The PD population will be used for analysis of all primary and secondary end points. Erroneously treated patients (eg, those randomized to one treatment but actually given the other) will be accounted for based on the actual treatment received.

Publication Strategy/Additional Information

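### The PK comparisons have no planned effect estimate or confidence interval, only a p<0.05 difference test, so a non-significant PK result would say little about whether exposure has changed

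*Combined protocol and SAP*

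**What the plan says.** All of this is in the combined protocol and SAP.

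- **Aim (Study Aim).** "The aim of this investigation is to rule out a DDI when cangrelor and prasugrel are concomitantly administered".
- **Role of PK (Background).** ExcelsiorLOAD2 is criticised partly because PK assessments, "pivotal to help elucidate a DDI, were not performed". The Study Rationale lists PK as one of three strands, with PD and receptor gene expression.
- **PK quantities (Description of laboratory assays, PK assay).** "The geometric mean area under the concentration-time curve through the sampling time of the last quantifiable prasugrel's active metabolite concentration" is to be calculated. Cmax and "time to Cmax (Tmax) of Pras-AM will be recorded".
- **Sampling (Study design).** "PK and PD assessments will be conducted at 7 time points".
- **Status (Study endpoints, sample size calculation and statistical analysis).** Apart from the primary PRU comparison, "all other end points will be considered exploratory and will include the comparisons of PD and PK parameters".
- **Method (same section).** ANCOVA with treatment and baseline platelet reactivity "will be used to evaluate the primary end point as well as all between-group comparisons at each time point". One-way ANOVA or Kruskal-Wallis is also named for continuous variables, just after a sentence on baseline characteristics.
- **Decision rule (same section).** "A 2-tailed p value of <0.05 will be considered to indicate a statistically significant difference", and this applies to every analysis.

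A least-squares mean difference with a 95% CI is specified for PRU only, and so is a margin (45 PRU). No between-group ratio, interval or log-scale model is given for PK.

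**The concern.** Showing that something has not changed is a different task from showing that it has. For PRU the plan respects this: it compares a confidence limit with a margin. For PK it does not. The only stated output is a test of difference, and when that test is non-significant the reader cannot tell whether exposure was similar or the sample was too small to show a fall.

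The method is also unclear. Read literally, the ANCOVA sentence sends metabolite concentrations at each time point through a model built for platelet reactivity. AUC, Cmax and Tmax are one value per patient, so they may fall under that sentence or under the ANOVA/Kruskal-Wallis sentence. The geometric mean AUC is a log-scale summary within each group, but nothing links it to a between-group comparison.

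What is at stake is the usefulness of the PK strand. PK is what would distinguish altered exposure from blocked receptor binding, and that requires an estimate of how much exposure changed.

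**Working it through.** **1. The plan's own sample size.** The only one is for PRU: SD 50, true difference 0, margin 45, 90% power, alpha 0.05. With one-sided alpha 0.05,

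n = 2 × [50 × (1.645 + 1.282) / 45]² = 21.1, so 22 per group.

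This matches the stated 22. (With one-sided 0.025, which a two-sided 95% CI implies, the formula gives 25.9, so 26; that is a separate matter.) Nothing here sizes the PK comparison, which simply inherits 22 evaluable patients per arm.

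**2. Assumption.** The documents give no between-patient variability for the active metabolite. I take a CV of 50%, with a range of 40% to 80%.

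**3. Formulas.** For a two-sample t test on log exposure with n = 22 per arm:

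- SD(log) = √ln(1 + CV²)
- SE = SD(log) × √(2/22), with 42 degrees of freedom
- noncentrality = ln(true ratio) / SE, where ln 0.8 = −0.223 and ln 0.7 = −0.357
- two-sided 5% critical value 2.018; miss rate = 1 − power, from the noncentral t
- 90% CI factor for the ratio = exp(1.682 × SE)

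**4. Results.**

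| Assumed CV | SD(log) | SE | Misses a 20% fall | Misses a 30% fall | 90% CI factor |
|---|---|---|---|---|---|
| 40% | 0.385 | 0.116 | 53% | 15% | ×/÷ 1.22 |
| 50% | 0.472 | 0.142 | 67% | 31% | ×/÷ 1.27 |
| 80% | 0.703 | 0.212 | 82% | 62% | ×/÷ 1.43 |

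Example at CV 50%, 20% fall: SE = 0.472 × 0.3015 = 0.142; noncentrality = −0.223 / 0.142 = −1.57; power 33%, so 67% missed.

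If all 28 randomized patients per arm gave PK data, the miss rates at CV 50% would still be 59% and 21%.

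**5. What an interval would add.** With an observed ratio of 1.00 and CV 50%, the 90% CI would be about 0.79 to 1.27. That tells the reader which falls are excluded and which are not. A p value alone does not.

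**6. What it would not add.** Taking 0.80 to 1.25 purely as illustrative limits (the documents set none), the chance that the 90% CI lies inside them with 22 per arm and a true ratio of 1 is about 20% at CV 40%, 2.5% at CV 50% and nil at CV 80%. The ratio is therefore an estimate, not a basis for an equivalence claim.

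**The case against.** The strongest case on the other side is that PK is declared exploratory, and that the formal test of interaction is PRU non-inferiority, which does have a CI and a margin. That stands, and it limits the weight of this point. Exploratory status excuses low power and the absence of multiplicity control. It does not make a difference test informative about absence of change, and an estimate with an interval is the usual output of an exploratory comparison.

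A reader might infer several stronger things that the documents do not support.

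- *That AUC and Cmax certainly go through the platelet-reactivity ANCOVA.* The text is ambiguous between that model and ANOVA/Kruskal-Wallis.
- *That the covariate distorts the PK comparison.* A pre-treatment covariate in a randomized comparison costs about one degree of freedom and does not bias it. Dropping it is tidiness.
- *That skewness is ignored.* A normality check, a rank test and a geometric mean are all mentioned. In simulation with 22 per arm, CV 50% and a true ratio of 0.7, power was 64% on the raw scale, 66% by ranks and 69% on the log scale. Choice of scale is a small part of the issue.
- *That a materially lower exposure would probably go undetected.* At CV 50% the log-scale test has 69% power for a 30% fall. A miss is more likely than not for a 20% fall at CV 40% or above, or for a 30% fall near the top of the assumed range.
- *That the investigators will report non-significance as no interaction.* Nothing in the documents says so. The plan simply does not guard against it.

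One further limit also stands. The Background describes the clopidogrel interaction as blocked receptor binding and suggests something similar for prasugrel. Unchanged exposure alone would not exclude that.

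**Conclusion.** The point holds as a gap in the PK analysis. With an aim of ruling out an interaction, the plan leaves PK with a p<0.05 rule, an unclear model, and no ratio or interval. A non-significant PK result would carry little information: with 22 per arm, a 20% fall in exposure would be missed in 53% to 82% of studies and a 30% fall in 15% to 62%. These figures rest on an assumed CV of 40% to 80%, log-normal exposure and complete PK data in 22 patients per arm. A lower CV would shrink them; at CV 30% they are 31% and 2%.

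A reader might conclude that the study therefore cannot address an interaction at all. That goes too far: the primary PRU comparison has its own interval and margin and does not depend on PK. The gap limits what the PK strand can contribute, and it is worth correcting because the correction needs no new data.

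**What to change.** In the statistical analysis section:

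1. Give PK its own paragraph, separate from the PD ANCOVA, and without baseline platelet reactivity as a covariate.
2. Analyse log-transformed AUC(0-tlast) and Cmax, and report the geometric mean ratio of group 2 to group 1 with a 90% CI. Label it an exploratory estimate, not an equivalence test.
3. Compare Tmax by a rank method and report the median difference.
4. State that a non-significant PK p value is not evidence of no interaction, and that unchanged exposure would not by itself exclude interaction through blocked receptor binding.

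The cost is wording only; the samples, assay and software stay the same. The downside is that the PK conclusion will look less certain than a bare p value, with a 90% CI of about ×/÷ 1.22 to 1.43 around the observed ratio over the assumed CV range.
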